6.2. Data Presentation Conventions

Unless otherwise specified, descriptive statistics for continuous variables include the number of patients with data (N), mean, standard deviation (SD), standard error (SE), first quartile (Q1), median, third quartile (Q3), minimum, and maximum. The same number of decimal places as in the observed value are presented when reporting minimum and maximum; 1 more decimal place than in the observed value is presented when reporting mean and quartiles; and 2 more decimal places than in the observed value are presented when reporting SD or SE.

Categorical data are presented using frequency counts and percentages. All percentages are rounded to 1 decimal place, unless otherwise specified. Percentages equal to 100 are presented as 100% and no percentages are presented for zero frequencies. Where individual variable values are missing, summaries of categorical data are based on reduced denominators (i.e., the denominators include only patients with available data), and the number of missing values is presented. For summaries of AEs and concomitant medications, the percentages are based on the total number of patients in each treatment group.

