The AYAME (402-006) study met the primary endpoint and key secondary endpoint; however, there was no separation in the occurrence of end-stage renal disease events between the 2 groups. Based on the AYAME (402-006) efficacy results, Kyowa Kirin and Reata have decided to discontinue clinical development of bardoxolone.

This decision was communicated to all sites on 10 May 2023, which is referred to as the study drug termination (SDT) date.

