9. SAFETY AND TOLERABILITY

Safety and tolerability are evaluated by AEs, SAEs, clinical laboratory test results, body weight, vital signs, 12-lead ECG findings. All analyses of the safety data are performed using the safety analysis set. Descriptive statistics are presented by treatment group assignment in the safety analysis set. Statistical testing is not performed for safety analyses unless otherwise specified. On-treatment values are summarized according to the analysis study windows in Section 6.5.2; Off-treatment values are summarized according to the analysis study windows in Section 6.5.2.1. Safety data summaries are grouped by treatment.

Continuous safety parameters (including selected clinical chemistries and vital signs) may be summarized using the methodology described in Section 8.4.1, and Section 8.5.1. Only the visit windows outlined in Table 4 and Table 5 are included in these analyses.

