9.1. Adverse Event Preferred Term and Body/Organ System Summary Tables

Treatment-emergent adverse events are summarized by treatment as defined by the safety analysis set. In addition to being summarized by treatment year, AEs are also summarized overall.

Treatment-emergent adverse events are events that either:

- Have a complete date of onset on or after the date of first dose and not more than 30 days after the date of the last dose of study drug, or
- Have no recorded date of onset with a stop date after the first dose of study drug, or
- Have no recorded date of onset and stop date.

General considerations for TEAE summaries are:

- Multiple events by PT and SOC are counted once only per patient for summaries of TEAE incidence.
- For summaries of TEAE incidence by severity, only the most severe event is counted per patient.
- For summaries of TEAE incidence by relationship, only the most strongly related event is counted per patient.
- A TEAE with a missing resolution date or incomplete date that is not identified as continuing is assumed to be continuing.
- For summaries of the number of TEAEs, all TEAEs are counted.

Off-treatment AEs (OTAEs) are events with a start date more than 30 days after last dose and not considered treatment emergent. Off-treatment AEs will be summarized separately.

Adverse Events are coded using MedDRA. In MedDRA, each verbatim term is mapped to a preferred term and high-level term (HLT), which is then mapped to a SOC.

The investigator grades the severity of the AEs as mild, moderate, or severe as defined in the study protocol. The investigator grades association or relatedness to the study medication according to criteria specified in Section 11.4 of the protocol.

As defined in the protocol, an SAE is an adverse event (occurring at any dose and regardless of causality) that:

- Results in death;
- Is life-threatening;
- Requires inpatient hospitalization or prolongation of existing hospitalization;
- Results in persistent or significant incapacity or substantial disruption of the ability to conduct normal life functions;
- Is a congenital anomaly or birth defect in an offspring of a patient taking study drug;
- Is an important medical event.

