9.1.2. Summaries of Adverse Events

Treatment-emergent adverse events and OTEAEs are summarized by treatment. For each treatment, SOC, and PT, the number and percentage of patients reporting an event is calculated. In summary tables, SOC is presented alphabetically and events within each SOC are presented by decreasing frequency count. Additionally, summary tables of events within PTs are presented by decreasing frequency count may be generated.

Summary tables (number and percentage of patients and events) of TEAEs (by SOC and PT) are provided by treatment as follows:

- All TEAEs
- All related TEAEs (definitely, probably, or possibly related)
- All TEAEs by severity
- All serious TEAEs (including deaths)
- All non-serious TEAEs
- All related serious TEAEs (including deaths)
- All TEAEs leading to permanent discontinuation of study drug
- All TEAEs leading to study drug interruption
- All TEAEs leading to dose de-escalation
- TEAEs by time to onset (≤ 12 weeks and > 12 weeks)
- TEAEs exhibited in $> 5\%$ of patients in either treatment group

Listings are provided showing:

- All AEs
- Deaths
- SAEs
- AEs leading to permanent discontinuation of study drug
- TEAEs leading to study drug interruption
- TEAEs leading to dose de-escalation

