9.3. Concomitant Medications

Concomitant medications are coded using the World Health Organization (WHO) drug dictionary for anatomical therapeutic chemical classification (ATC) and preferred drug name. A patient who used multiple medications is counted only once for each ATC and preferred drug name. ATC and preferred drug name within each ATC are sorted alphabetically. Coded concomitant medications are summarized by treatment, WHO ATC class and preferred name. Percentages are based on the number of patients in the safety analysis set. Each summary is ordered by descending order of incidence of ATC class and preferred name within each ATC class. Concomitant medications will be summarized by treatment year and overall.

A concomitant medication is any medication taken at the time of first study treatment or a medication that was started after the start of study drug dosing. Specifically, concomitant medications are medications

- that are continued from screening and continued after the first study drug dosing, or
- that have start dates or stop dates within the treatment period, or
- that start before treatment end and have no end date.

Medications with an end date on the date of first study drug administration are not considered concomitant medications. Patients who take excluded medications (defined in the Protocol Section 9.3.1) during the study are listed.

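### AE percentages by treatment year and for onset after 12 weeks count patients no longer at risk as event-free; add an at-risk N and exposure-adjusted rates

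*SAP*

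**What the plan says.** SAP 6.2 lets most categorical summaries use reduced denominators when data are missing, then sets a separate rule for two kinds of table: "For summaries of AEs and concomitant medications, the percentages are based on the total number of patients in each treatment group". It makes no exception for tables restricted to part of the treatment period.

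SAP 9 names the population: "All analyses of the safety data are performed using the safety analysis set". Under SAP 6.3 that means every enrolled patient with at least one dose.

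SAP 9.1 plans period-specific tables: "In addition to being summarized by treatment year, AEs are also summarized overall". SAP 9.1.2 adds "TEAEs by time to onset", split at 12 weeks. The measure is a count with a crude percentage: "For each treatment, SOC, and PT, the number and percentage of patients reporting an event is calculated". Neither section gives an at-risk number or a person-time rate.

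SAP 9.1 closes the treatment-emergent window 30 days after last dose. Later events are summarised separately as off-treatment events.

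SAP 2 records the sponsor's decision to end development of the drug: "This decision was communicated to all sites on 10 May 2023". The SAP calls this the study drug termination date.

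**The concern.** A column for treatment Year 2, or for onset after 12 weeks, is where a reader looks for late harm, and it is naturally read as the risk among patients still being treated then. Two groups cannot contribute to it: patients who stopped early, and patients whose dosing was cut short by the May 2023 termination. Under SAP 6.2 both groups count as treated and event-free. Late-period percentages are then low in both arms. If one arm has more early stopping, its late-period percentage is lowered more and the comparison shifts in its favour. Safety and tolerability is part of the primary objective (SAP 3.1.1), so these tables carry some weight even though they are descriptive.

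**Working it through.** **The plan's own figures.** The SAP gives no number for AE percentages. The only related figure is the sample size in SAP 4.3.1: 850 patients, 1:1, difference 2.3, SD 12, two-sided 0.05. With 425 per arm, 2.3/(12 × √(2/425)) = 2.79, and 2.79 − 1.96 = 0.83, which gives power 79.8% against the stated 80% or so. It reproduces, and it is used here only for the planned arm size.

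**Who is out of the window.** The window closes on day of last dose + 30 (SAP 9.1).
- Onset after 12 weeks starts on Day 85. A last dose on or before Day 54 closes the window by Day 84, so no event can count.
- Year 2 is taken to start on Day 365; this is an assumption, because the SAP does not define treatment year. A last dose on or before Day 334 closes the window by Day 364.

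**Effect on one arm.** Let s be the share of the arm out of the window at the start of the period, and p the risk among the rest. Reported percentage = p × (1 − s). For p = 10%:
- s = 5%: 9.5%
- s = 10%: 9.0%
- s = 20%: 8.0%
- s = 30%: 7.0%
- s = 50%: 5.0%

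The relative understatement equals s. These values of s are assumed.

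**Effect on the comparison.** Reported ratio = true ratio × (1 − s_bard)/(1 − s_pbo). Illustrations only, placebo v bardoxolone:
- s = 30% in both arms: factor 1.00, so the ratio is untouched.
- s = 5% v 10%: factor 0.90/0.95 = 0.95.
- s = 10% v 30%: factor 0.70/0.90 = 0.78. An equal 10% risk appears as 9.0% v 7.0%, and a true 10% v 12% appears as 9.0% v 8.4%, which reverses the direction.
- s = 5% v 15%: a true 10% v 12% appears as 9.5% v 10.2%, so the excess shrinks but keeps its direction.

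**Contribution of the sponsor's termination.** Assume last doses on 10 May 2023, so the window closes on 9 June 2023. Day 365 is 364 days after first dose, so a patient must have been first dosed by 10 June 2022 to reach it. SAP front matter dates first enrolment to May 2019. If accrual ran to May 2023 (48 months, assumed), the last 11 months are excluded:
- uniform accrual: 11/48 = 23%;
- linearly rising accrual: 1 − (37/48)² = 1 − 0.594 = 41%.

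With 1:1 randomisation this share is expected to be about the same in both arms.

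**The case against.** The strongest reply is that the crude percentage is not wrong. Events in the period divided by all treated patients is a legitimate share of the safety set, and a common N lets the early and late onset columns be read side by side. That stands: the figure is low only when read as risk among those still at risk. It is a reason to keep the present percentage, not a reason to show nothing else.

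Second, an at-risk denominator has a bias of its own. Patients still in the window at Day 85 or Day 365 are selected after randomisation, and those who tolerated the drug poorly may have left. This also stands, so a reader should not infer that the at-risk percentage is the unbiased answer.

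Third, much of the information is already planned. SAP 7.1 counts patients dosed at or after Week 52 and patients on and off treatment by visit, and SAP 9.2 gives exposure beyond 16, 24, 48, 72 and 96 weeks. A reader could approximate a Year 2 denominator from the 48-week category. None of these exposure categories matches the Day 54 cut-off for the 12-week split, and a reader should not have to assemble a denominator from other tables.

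Fourth, safety summaries are descriptive and no decision rule uses them. This limits the weight of the point.

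A reader might also infer that the tables will flatter bardoxolone. The documents do not support that. They give no stopping rates by arm, and the one known large source of truncation, the sponsor's termination, applies to both arms alike.

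**Conclusion.** The point holds as a matter of how the tables are read. The late-period percentages understate risk among patients still at risk by exactly s. They distort the arm ratio only to the extent that s differs between arms; with equal s, only the absolute rates are low.

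The size is unknown. The 23% to 41% range rests on assumed accrual, on Year 2 starting at Day 365 and on last doses at 10 May 2023. Early stopping for other reasons would add to it. Every between-arm example above is illustrative.

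It is tempting to extend the same remedy to concomitant medications, since SAP 6.2 covers them and SAP 9.3 says "Concomitant medications will be summarized by treatment year and overall". That does not follow. SAP 9.3 defines them without the 30-day window, and Protocol 9.10.4 collects all medications for 12 weeks after an early last dose and kidney-relevant ones beyond that. The AE window is therefore the wrong at-risk definition for that table.

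One reservation: the available SAP text has no Section 9.6, so an exposure-adjusted AE table there cannot be excluded. Sections 9.1 and 9.1.2, which define these tables, contain none. I would label this a cheap improvement.

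**What to change.** For the by-year and after-12-week AE tables in SAP 9.1 and 9.1.2:
- keep the percentage of all treated patients;
- add, by arm, the number of safety-set patients still in the treatment-emergent window at the start of the period, with the percentage on that number;
- add exposure-adjusted incidence per 100 patient-years of treatment-emergent risk time, by period and overall;
- state the study day on which treatment Year 2 begins;
- footnote that the at-risk patients are a subset selected after randomisation, made up of those who stayed on drug.

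Add a matching exception to SAP 6.2. Leave the concomitant medication tables in SAP 9.3 outside this change.

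The cost is SAP wording, table headers and a few more columns; dose and event dates are already collected. Late-event percentages on the at-risk number will look larger than those on all treated patients, and the two need clear labels so that they are not confused.

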6.3. Analysis Populations

Table 3 lists the analysis populations in the study.

Table 3: ANALYSIS POPULATION DEFINITION

Analysis Population	Definition
ITT (Intent-to-Treat)	All enrolled patients categorized by their randomized treatment group (whether or not they received study drug).
Safety	All enrolled patients who received at least 1 dose of study drug. The safety population is used for evaluation of safety variables. Patients who received 1 dose of bardoxolone methyl will be classified in the bardoxolone methyl group. Patients who received at least 1 dose of placebo and no dose of bardoxolone methyl will be classified in the placebo group.

6.4. Baseline Definitions

Baseline values are defined as the last non-missing assessment prior to the first study drug administration, unless otherwise specified below. If the first study drug administration occurs after the date of randomization, the last measurement prior to the first study drug administration is considered the Day 1 measurement for the calculation of baseline. If the first study drug administration date is not present, the baseline values are the last non-missing assessment on or prior to the Day 1 visit date.

When assessment time is not available, assessments that are collected on the same date as the first date of study drug administration are considered to occur before the first dose of study drug administration.

6.4.1. Age

Baseline age is defined as the age at consent (Screen A).

6.4.2. Estimated Glomerular Filtration Rate

Baseline eGFR is defined as the average of Screening and Day 1 eGFR measurements, calculated as shown below:

- Screening eGFR=average of the last 2 eGFR measurements collected prior to the Day 1 eGFR collection
- Day 1 eGFR=the measurement after screening but on or before the date of first study drug administration
- Baseline eGFR=(0.5×Day 1 eGFR)+(0.5×Screening eGFR)

If there are only 2 observations available, then the average of the 2 values is used as baseline. Since patients must have Screen A and Screen B eGFR values within a percent difference $\leq 25\%$ to be eligible for enrollment, the variability of Screening eGFR is mediated by the study inclusion/exclusion criteria. Furthermore, the Screening eGFR value may be collected up to

3 months prior to study entry. The Day 1 eGFR value carries greater weight in the baseline eGFR calculation to account for the reduced variability in the screening eGFR values.

6.4.3. Serum Creatinine

Baseline serum creatinine (SCr) is defined in the same way as baseline eGFR (Section 6.4.2).

6.4.4. Safety Assessments

Baseline for continuous safety assessments (i.e., vital sign assessments, weight, body mass index [BMI], and laboratory measurements) is defined as the average value of measurements collected up through the date of, but not after, first study drug administration.

6.4.5. Urine Albumin to Creatinine Ratio

Baseline ACR is defined as the last ACR value prior to the first study drug administration. Baseline ACR is summarized using the geometric mean of ACR values.

6.4.6. Natural log (ACR)/eGFR

Baseline of natural log (ACR)/eGFR is defined as the ratio of the natural log of baseline ACR (Section 6.4.5) divided by baseline eGFR (Section 6.4.2).

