Notably, Reata's Asian development partner, Kyowa Kirin Co., Ltd, demonstrated that bardoxolone methyl treatment resulted in a significant improvement in measured GFR, as assessed by inulin clearance, in Japanese patients with CKD and type 2 diabetes. Improvements in other measures of renal function, including BUN, uric acid, and phosphorus, have also been consistently observed, providing further evidence that observed changes in eGFR reflect true improvements in kidney function.

Bardoxolone methyl was also shown to significantly increase eGFR in patients with CKD due to Alport syndrome after 12 weeks of treatment. The increases in eGFR from baseline at Week 12 were shown to be sustained through 48 weeks of treatment (10.4 mL/min/1.73 m^2; n=25; p<0.0001) and partially retained four weeks after withdrawal of study drug (4.1 mL/min/1.73 m^2; p<0.001). The clinical activity of bardoxolone methyl in Alport syndrome and diabetic nephropathy, two diseases with distinct etiologies (type IV collagen defects versus hyperglycemia, respectively), suggests that the anti-inflammatory and anti-fibrotic effects of bardoxolone methyl target the common final pathways contributing to GFR loss in multiple forms of chronic kidney diseases.

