Most recently, bardoxolone methyl was studied in a Phase 2 trial (study 402-C-1702, PHOENIX, NCT03366337) in patients with four rare forms of CKD: genetically-confirmed autosomal dominant polycystic kidney disease (ADPKD), biopsy-confirmed IgA nephropathy (IgAN), diabetic nephropathy secondary to type 1 diabetes (T1D), or biopsy-confirmed focal segmental glomerulosclerosis (FSGS). In the cohort of patients with ADPKD with PKD1 mutations, treatment with bardoxolone methyl significantly increased eGFR after treatment with 12 weeks (mean ± SE: 9.3 ± 1.4 mL/min/1.73 m^2; n=31; p<0.0001). The improvements were consistent, and 27 of the 28 (96%) patients with data at Week 12 had improvements from baseline in eGFR. The increases were observed across multiple subgroups including age, gender, baseline eGFR, and baseline albumin to creatinine ratio (ACR). Historical eGFR data for 29 of the 31 patients showed that these patients' kidney function was declining at an average annual rate of 4.8 mL/min/1.73 m^2 prior to study entry. Therefore, the improvements in eGFR after 12 weeks of treatment with bardoxolone methyl represents a recovery of approximately two years of average eGFR loss in ADPKD patients. Thus, the magnitude and durability of eGFR increases with bardoxolone methyl could provide a meaningful therapeutic benefit, even over the sole available therapy (tolvaptan) in ADPKD.

**Table 3: Cross-Study Comparison of Increases in eGFR, Inulin Clearance, and Creatinine Clearance with Bardoxolone Methyl Treatment**

Study	Phase/ Country	Study Population	# of Patients	Treatment Duration	$\Delta$ eGFR (mL/min/1.73m  ) a
CKD Studies					
402-C-0801 (Stratum 1) (open label)	2a/ US	Age $\geq$ 18, Diabetic nephropathy	60	28 days	6.7 (p<0.001)
402-C-0801 (Stratum 2) (open label)	2b/ US	Age $\geq$ 18, Diabetic nephropathy	20	56 days	7.2 (p<0.001) CrCl also sig. increased
402-C-0804 (BEAM)	2/ US	Age $\geq$ 18, T2D and CKD	227	52 weeks	8.6 at WK52 (p<0.001 vs PBO)
402-C-0902	2/ US	Age $\geq$ 18, T2D and CKD	131	85 days	6.5 (p<0.001)
402-C-0903 (BEACON)	3/ Global	Age $\geq$ 18, T2D and Stage 4 CKD	2185	Median: 7 months with 522 patients through Week 48	6.4 (p<0.001 vs PBO) CrCl also significantly increased
402-C-1102	1/US	Age $\geq$ 18, T2D and Stage 3b and Stage 4 CKD	24	56 days	9.0 (p<0.05)
RTA402-005 (TSUBAKI)	2/ Japan	Age $\geq$ 20, T2D and Stage 3 and 4 CKD	120	16 weeks	6.6 (inulin GFR) (p=0.008 vs PBO)

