#### **5.1.2.6. Increases in Urinary Protein**

Increases in urinary albumin have been observed in some patients treated with bardoxolone methyl with CKD and type 2 diabetes. The increases are likely due to bardoxolone methyl's pharmacological modulation of tubular protein reabsorption and have not been associated with interstitial fibrosis or injury. In preclinical studies, bardoxolone methyl has been shown to downregulate the primary proteins involved in protein reabsorption in the proximal tubules: the megalin-cubilin complex. Moreover, the magnitude of observed eGFR increases with bardoxolone methyl treatment is thought to reduce the residence time of protein in the proximal tubules, thereby reducing protein reuptake and increasing urinary protein levels. Therefore, increased eGFR, together with decreased megalin expression, is thought to result in decreased fractional absorption of albumin and increased urinary excretion of albumin. Consistent with bardoxolone methyl-mediated protection in preclinical models of protein-overload-induced nephropathy, these pharmacological effects are thought to reduce protein overload and secondary nephropathy caused by excessive albumin uptake and therefore are not associated with tissue injury and interstitial fibrosis.

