6.5.7. ACR adjusted for eGFR

To evaluate ACR after adjusting for filtration rate, $\ln(\text{ACR})/\text{eGFR}$ (Sections 6.5.5 and Section 6.5.4) is assessed.

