9.5.1. Continuous Summaries of Laboratory Results

Laboratory evaluations and change from baseline are summarized by treatment, laboratory category (hematology, chemistry, urinalysis, and microscopy), test, and study visit using continuous statistics. The eGFR results are calculated using formulas described in Section 6.5.4.

Chemistry values (including eGFR) collected at the following visits will be averaged.

- Week 104 A and Week 104 B
- Week 108 A and Week 108 B
- Week 112 A and Week 112 B

Box plots and line graphs are generated for selected laboratory test results, such as eGFR, ACR, alanine aminotransferase (ALT), aspartate aminotransferase (AST), TBL, BNP, blood urea nitrogen, uric acid, magnesium, creatinine, and creatine kinase (CK). Line graphs include mean \pm SE over time for both the observed values and for change from baseline.

Summaries of continuous statistics are provided for the following urinalysis parameters: albumin, creatinine, pH, erythrocytes, and specific gravity. Qualitative lab results are included in the listings but are not summarized. Laboratory results that are above or below normal limits are flagged in the listings. Summaries of ACR (Section 6.5.5) will use the geometric mean (with standard error) with 95% confidence intervals instead of the arithmetic mean and will display ACR results in original units of mg/g. Changes from baseline in ACR are calculated as the ratio of each visit to baseline and reported as the post-baseline/baseline ratios and are summarized by geometric means with 95% confidence intervals at each time point.

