9.5.1.1. Natural log (ACR)/eGFR

Mean ratios of natural log (ACR)/eGFR (Section 6.4.6) are summarized at each time point. The ratio of natural log (ACR)/eGFR by analysis visit is summarized by arithmetic means.

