9.5.2. Categorical Summaries of Laboratory Results

Select laboratory parameters will be summarized using shift tables. Shift tables are summarized by treatment, laboratory category (hematology, chemistry, urinalysis, and microscopy), and laboratory test and present shifts from baseline status (Normal, Low, High) to worst on study treatment status (Normal, Low, High). The worst abnormality values are defined as the maximum values while on study treatment (i.e., up to <21 days after last dose), with the exception of magnesium and hemoglobin. The worst abnormal values for magnesium and hemoglobin are defined as the minimum values while on study treatment (i.e., up to <21 days after last dose).

Additionally, laboratory parameters of specific interest (ALT, AST, ACR, BNP) are summarized using shift tables that summarize shifts from (1) baseline status to end of treatment status, (2) worst on-treatment status to worst off-treatment status, (3) worst on-treatment status to end of study, and (4) baseline status to worst on-treatment status 5) baseline to worst off-treatment, and (6) worst on-treatment status to best (lowest) off-treatment status. The number and percentage of patients are summarized. For ACR, summaries will present shifts from/to the categories listed in Section 6.5.5.1. For ALT and AST, summaries will present shifts from/to the following categories:

- \leq ULN
- $>$ ULN to $<3 \times$ ULN
- $\geq 3 \times$ ULN to $<5 \times$ ULN
- $\geq 5 \times$ ULN to $<10 \times$ ULN
- $\geq 10 \times$ ULN to $<20 \times$ ULN
- $\geq 20 \times$ ULN

For BNP, summaries will present shifts from/to the following categories:

- <100 pg/mL
- ≥ 100 pg/ml to <200 pg/ml
- ≥ 200 pg/ml to <400 pg/ml
- ≥ 400 pg/ml

In addition, a summary table is provided for the number and percentage of patients meeting a following pre-specified threshold level at any time during the study:

- ACR >3500 mg/g
- Magnesium <1.3 mEq/L (0.65 mmol/L)
- BNP >200 pg/mL
- NT-proBNP >1000 pg/mL

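### The SAP's filtration-adjusted albuminuria index, ln(ACR)/eGFR, does not make that adjustment and can fall when ACR per unit of filtration is unchanged or higher.

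*SAP*

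**What the plan says.** Three short SAP sections set up the index.

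- **6.4.6** gives the baseline form: it "is defined as the ratio of the natural log of baseline ACR (Section 6.4.5) divided by baseline eGFR". This rules out reading it as the log of the quotient ACR/eGFR.
- **6.5.7** uses the same form after baseline and states the purpose: "To evaluate ACR after adjusting for filtration rate".
- **9.5.1.1** gives the reporting: "The ratio of natural log (ACR)/eGFR by analysis visit is summarized by arithmetic means".

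Unadjusted ACR is handled separately. In 9.5.1, "Changes from baseline in ACR are calculated as the ratio of each visit to baseline and reported as the post-baseline/baseline ratios", with geometric means and 95% confidence intervals. In 9.5.2, "laboratory parameters of specific interest (ALT, AST, ACR, BNP) are summarized using shift tables", and patients with ACR above 3500 mg/g are counted.

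Two parts of the protocol explain why an adjusted measure is wanted. Section 5.1.1 reports that in the ADPKD cohort "treatment with bardoxolone methyl significantly increased eGFR after treatment with 12 weeks", by a mean of 9.3 mL/min/1.73 m². Section 5.1.2.6 states: "Increases in urinary albumin have been observed in some patients treated with bardoxolone methyl with CKD and type 2 diabetes", and attributes this partly to the higher eGFR.

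**The concern.** A filtration-adjusted albuminuria measure should stay still when ACR moves in step with eGFR and rise when ACR rises faster. Dividing a logged quantity by an unlogged one does neither. A small relative change in ACR moves the index by only 1/ln(ACR) of that change, while a relative change in eGFR counts in full.

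The drug is expected to raise eGFR, and urinary albumin is a named safety topic. The question for this index is whether a rise in ACR is more than higher filtration would explain. An index that a higher eGFR pulls down can show a decline in the active arm while ACR relative to filtration is stable or rising.

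**Working it through.** The documents give no numerical value for this index, so there is no plan figure to reproduce.

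**Inputs**
- eGFR gain d: +9.3 (phase 2 ADPKD cohort, Week 12, n=31) and +4.1 (Alport cohort, described as "partially retained four weeks after withdrawal of study drug"). As a check at low eGFR, +7.4 from a baseline of 32.4 (phase 2b diabetic CKD study, Week 52). All are in Protocol 5.1.1.
- Baseline eGFR: 30 and 90 (the ends of the eligibility range) and 50 (assumed).
- Baseline ACR: 30, 100, 300 and 1000 mg/g (assumed). Entry requires ACR of at most 2500 mg/g.

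**1. ACR in proportion to eGFR.** Write g for eGFR and ACR = k·g. The index is ln(k·g)/g, with derivative (1 − ln ACR)/g². This is negative whenever ACR exceeds e = 2.72 mg/g.
- Before: ln(300)/50 = 0.11408.
- After (eGFR 59.3, ACR 300 × 59.3/50 = 355.8): ln(355.8)/59.3 = 0.09906, a fall of 13.2%.
- The same proportional case with +9.3 at ACR 300 gives a fall of 20.1% from eGFR 30 and 7.8% from eGFR 90.

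**2. ACR rising faster than eGFR.** ACR 300 to 600 with eGFR 50 to 59.3 multiplies ACR/eGFR by 2/1.186 = 1.686. The index is ln(600)/59.3 = 0.10787, a fall of 5.4%. From ACR 30 to 60 the rise is not hidden: ln(30)/50 = 0.06802 and ln(60)/59.3 = 0.06904, up 1.5%.

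**3. Break-even.** The index is flat when ln(ACR1)/g1 = ln(ACR0)/g0, so ACR must rise by the factor ACR0^(d/g0) before the index stops falling.

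| Baseline eGFR, gain | Exponent d/g0 | ACR 30 | ACR 100 | ACR 300 | ACR 1000 |
|---|---|---|---|---|---|
| 30, +9.3 | 0.310 | 2.87 | 4.17 | 5.86 | 8.51 |
| 32.4, +7.4 | 0.228 | 2.17 | 2.86 | 3.68 | 4.84 |
| 50, +9.3 | 0.186 | 1.88 | 2.36 | 2.89 | 3.61 |
| 90, +9.3 | 0.103 | 1.42 | 1.61 | 1.80 | 2.04 |
| 50, +4.1 | 0.082 | 1.32 | 1.46 | 1.60 | 1.76 |

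**4. When a doubling of ACR is hidden.** Setting the break-even factor to 2 gives ACR0 = 2^(g0/d). With +9.3 the threshold is 2^(30/9.3) = 9, 2^(50/9.3) = 42 and 2^(90/9.3) = 819 mg/g. With +4.1 from eGFR 50 it is 2^(50/4.1), about 4,700 mg/g, which is beyond the entry limit.

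**5. Dependence on units.** SAP Figure 2 equates 300 mg/g with 30 mg/mmol. For one patient whose ACR doubles from that level while eGFR goes from 50 to 59.3, the index falls 5.4% in mg/g (step 2) and rises 1.5% in mg/mmol (ln 30/50 = 0.06802 to ln 60/59.3 = 0.06904). The direction of change depends on the reporting unit.

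**6. Falling eGFR.** With eGFR 50 to 45 and ACR 300 to 270, ACR/eGFR stays at 6.00, but the index rises 9.1% (0.11408 to 0.12441). Declining eGFR on placebo would therefore widen the apparent contrast between arms.

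**7. The alternative.** ln(ACR) − ln(eGFR) goes from 1.792 to 1.792 in step 1. In step 2 it goes from 1.792 to 2.314, and exp(0.522) = 1.69, the true rise in ACR/eGFR.

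**The case against.** The strongest reply is that little depends on this index. Safety summaries carry no formal testing unless specified, development of the drug had been stopped before this SAP was dated, and no readable endpoint or decision rule uses the index. ACR and eGFR are both tabulated and plotted over time, so a reader can compare them directly. All of that is correct and limits the consequence. It does not make the label in 6.5.7 accurate, and no other readable summary reports ACR relative to filtration.

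A second reply is that adjustment need not mean proportional scaling. Protocol 5.1.2.6 also points to reduced tubular reabsorption, which need not follow eGFR. This is fair, and the replacement should state its assumption. The unit dependence in step 5, however, is a defect under any scaling.

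A third is that the largest figures apply a cohort mean gain of +9.3 at eGFR 30, where the gain is not known. That also stands. With +7.4 from 32.4, in a different disease, break-even is about 2.2- to 4.8-fold instead of 2.9- to 8.5-fold, and a doubling is hidden above about 21 mg/g (2^(32.4/7.4)) instead of 9. The direction is the same.

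Finally, below 2.72 mg/g the effect reverses, and below 1 mg/g the index is negative (SAP 6.5.5 allows 0.1 mg/g). This limits any one-directional account, but it is a further fault of the index.

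**Conclusion.** The concern holds. As defined, ln(ACR)/eGFR does not adjust ACR for filtration rate, and the name and purpose given in 6.5.7 would mislead. With eGFR rising from 50 to 59.3, it stays flat or falls until ACR has risen 1.9-fold (baseline 30 mg/g) to 3.6-fold (baseline 1000 mg/g). Off treatment, with +4.1, the range is 1.3- to 1.8-fold, and no doubling is hidden within the entry limit.

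These sizes rest on assumed eGFR gains and baseline values and are worked for single patients. The documents give no ACR distribution for this trial, so the share of patients in the affected range, and the effect on an arm mean, are unknown. In the readable text the fault is confined to one descriptive safety summary. The primary analysis is untouched, and the unadjusted ACR summaries keep raw rises visible. It should be corrected because the error is definite, tends to reassure when eGFR rises, and is cheap to remove.

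**What to change.** In SAP 6.4.6, 6.5.7 and 9.5.1.1, define the adjusted measure as ln(ACR) − ln(eGFR), with baseline formed as ln(baseline ACR) − ln(baseline eGFR). Report it by visit as the geometric mean ratio to baseline with a 95% CI, the format 9.5.1 already uses for ACR. State in 6.5.7 that this assumes ACR scales in proportion to eGFR. If the existing ratio is kept for continuity, list it second and do not describe it as adjusted for filtration rate.

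The cost is one derived variable and wording in three sections, using data already collected. Some comparability is lost with any earlier summaries that used the old ratio. If the SAP is already final, SAP section 2 allows the change to be documented in the CSR.
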